# **11 STATISTICAL CONSIDERATIONS**

This is an open label, phase II clinical trial to evaluate the efficacy of isavuconazole prophylaxis in adult patients with newly diagnosed AML/MDS and neutropenia. A total of 100 patients will be accrued from M.D. Anderson Cancer Center (MDACC), at a rate of 5 patients per month. The primary endpoint is the incidence of proven or probable invasive fungal infections (IFI) for up to 100 days from prophylaxis initiation. Occurrence of IFIs will be assessed during the period of prophylaxis (see section 6.2) and up to 100 days from prophylaxis initiation.

The method of Thall, Simon and Estey will be used for futility and toxicity monitoring in this study.

A 10% frequency of IFIs is observed in general in AML during remission induction. The current standard of care is posaconazole prophylaxis in preventing IFI. Assuming that isavuconazole is as effective as posaconazole, subjects receiving isavuconazole would be expected to have a 5% rate of IFIs. We assume a priori for IFI rate, p (IFI) ~ beta (0.1, 1.9). The following futility stopping rule will be applied in cohort sizes of 10, starting from the 10th patient: the trial will be stopped if Pr(p(IFI) > 0.05 | data) > 0.87. That is, we will stop the trial for new patient enrollment if at any time during the study we determine that there is a more than 87% chance that the IFI rate is more than 5%. Stopping boundaries corresponding to the IFI monitoring rule are shown in Table 1 below. The operating characteristics for the monitoring are summarized in Table 2. Multe Lean Desktop (version 2.1) was used to generate the IFI stopping boundaries and the OC table. We will submit a futility/toxicity summary to the IND Office Medical Monitor, after the first ten patients have completed study therapy, or administration is discontinued, whichever comes first; and every ten patients thereafter.

Number of patients	No. of patients with IFIs that will lead to the trial being stopped
10	2-10
20	3-20
30	4-30
40-50	5-50
60	6-60

Table 1. IFI stopping boundaries in cohort sizes of 10.

70-80	7-80
90	8-90

Table 2. Operating characteristics for IFI monitoring in cohort sizes of 10 (max sample size = 100).

True IFI rate	Prob(stop the trial	Average sample
	early)	size
0.01	0.005	99.6
0.02	0.02	98.1
0.03	0.06	95.3
0.04	0.13	90.9
0.05	0.23	84.9
0.06	0.35	77.7
0.07	0.48	69.8
0.08	0.60	61.8
0.09	0.71	54.2
0.1	0.80	47.3
0.15	0.98	25.5

Toxicity will be monitored in all patients. Denote the probability of toxicity by p (Tox), where toxicity is defined as any Grade  $\geq$ 3 clinically relevant non-hematologic toxicity, grade  $\geq$ 4 hematologic toxicity lasting  $\geq$ 6 weeks with a hypocellular bone marrow and <5% blasts or a serious adverse event (SAE) that is definitely, probably or possibly related to the study drug (AEs will be graded according to the Common Terminology Criteria for Adverse Events (CTCAE) version 4.0). We assume a priori for toxicity rate, p (tox) ~ beta (0.6, 1.4). The following toxicity stopping rule will be applied in cohort sizes of 10, starting from the 10th patient: the trial will be stopped if Pr(p(tox)> 0.3 | data) > 0.9. That is, we will stop the trial for new patient enrollment if at any time during the study we determine that there is a more than 90% chance that the toxicity rate is more than 30%. Stopping boundaries corresponding to the toxicity monitoring rule are shown in Table 3 below. The operating characteristics for the monitoring are summarized in Table 4. Again, Multe Lean Desktop (version 2.1) was used to generate the toxicity stopping boundaries and the OC table.

Table 3. Toxicity stopping boundaries in cohort sizes of 10.

Number of patients	No. of patients with toxicity that will lead to the tria being stopped			
10	6-10			
20	9-20			
30	13-30			
40	16-40			
50	20-50			
60	23-60			
70	27-70			
80	30-80			
90	33-90			

Table 4. Operating characteristics for toxicity monitoring in cohort sizes of 10 (max sample size = 100).

True toxicity rate	Prob(stop the trial early)	Average sample size
0.1	0.0002	99.9
0.2	0.02	98.6
0.3	0.26	83.1
0.4	0.86	43.5
0.6	1.0	14.4

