# 4.1.2 Secondary

- 4.1.2.1 To evaluate the incidence of IA within 100 days of beginning isavuconazole prophylaxis in newly diagnosed patients with AML/MDS receiving intensive chemotherapy or other therapies.
- 4.1.2.2 To evaluate the incidence of other IFIs within 100 days of beginning isavuconazole prophylaxis in newly diagnosed patients with AML/MDS receiving intensive chemotherapy or other therapies.
- 4.1.2.3 To evaluate the composite outcome of treatment success vs. failure in this patient population (Definition of treatment failure: occurrence of proven or probable IFI, receipt of any other systemic antifungal agent for ≥4 days for suspected IFI, occurrence of an AE possibly or probably related to the study drug resulting in discontinuation of treatment, or withdrawal from the study with no additional follow-up).
- 4.1.2.4 To measure the overall survival (OS) of study participants.
- 4.1.2.5 To measure the IFI-free survival of study participants.
- 4.1.2.6 To document the time to death from any cause in the study population.
- 4.1.2.7 To document the time to death related to IFI in the study population.
- 4.1.2.8 To document the time to diagnosis of proven or probable IFI in the study population.
- 4.1.2.9 To document the time to initiation of empiric anti-fungal therapy in the study population.
- 4.1.2.10 To characterize the safety, tolerability and AE profile of isavuconazole in the prophylactic setting.

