# **12 REPORTING REQUIREMENTS**

These guidelines will be followed for the recording and reporting of adverse events and SAEs.

- 1. Baseline events will be recorded in the medical history section of the case report form (CRF) and will include the terminology event name, grade and start date of the event.
  - a. Baseline events are any medical condition, symptom, or clinically significant lab abnormality present before the informed consent form (ICF) is signed.
    - i. Hematologic laboratory abnormalities will not be recorded as baseline events for patients with acute leukemia, myelodysplastic syndrome, chronic lymphocytic leukemia, or chronic myeloid leukemia in blast phase.
    - ii. If exact start date is unknown, month and year or year may be used as the start date of the baseline event.
- 2. The maximum grade of the adverse event will be captured per course of protocol defined visit date.
- 3. These adverse events will be recorded in the case report form:
  - a. Any grade adverse event that is possibly, probably or definitely related to the study drugs(s).
  - b. All serious adverse events regardless of attribution to the study drug(s).
  - c. Any grade adverse event regardless of attribution to the study drug(s) that results in any dose modification.
- 4. Hematologic adverse events will not be recorded or reported for studies in patients with acute leukemia, myelodysplastic syndrome, chronic lymphocytic leukemia, or chronic myeloid leukemia in blast phase except for:
  - a. Prolonged myelosuppression as defined by the NCI-CTCAE criteria specific for leukemia, e.g., marrow hypocellularity on day 42 or later (≥6 weeks) from start of therapy without evidence of leukemia (<5% blasts), or that results in dose modifications, interruptions or meets the protocol definition of DLT or SAE.
- 5. SAEs will be reported according to institutional policy.
- 6. Protocol specific language regarding the recording and reporting of adverse and serious adverse events will be followed in the event of discordance between the protocol and Leukemia Department-specific adverse event recording and reporting guidelines.

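### Does the toxicity stopping rule fail because it does not say whether drug-relatedness applies to all three event types?

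*Combined protocol and SAP*

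**What the plan says.** Section 11 defines the toxicity to be monitored as any one of three things:

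- grade 3 or worse "clinically relevant non-hematologic toxicity";
- grade 4 or worse hematologic toxicity that persists for at least six weeks "with a hypocellular bone marrow and <5% blasts";
- as the last item, which alone carries an attribution phrase: "or a serious adverse event (SAE) that is definitely, probably or possibly related to the study drug".

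The prior is beta(0.6, 1.4). Enrollment stops if the posterior probability that the toxicity rate exceeds 30% is above 0.9, checked every ten patients. Table 3 gives the boundaries and Table 4 the operating characteristics. On reporting, the section says: "We will submit a futility/toxicity summary to the IND Office Medical Monitor", first after ten patients and then after every further ten.

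Section 12, item 3, lists what goes on the CRF:

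- 3a: "Any grade adverse event that is possibly, probably or definitely related to the study drugs(s";
- 3b: "All serious adverse events regardless of attribution to the study drug(s";
- 3c: "Any grade adverse event regardless of attribution to the study drug(s) that results in any dose modification".

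Item 4 keeps hematologic events off the CRF, but 4a excepts prolonged myelosuppression. The treatment-failure definition in 4.1.2.3 includes "occurrence of an AE possibly or probably related to the study drug resulting in discontinuation of treatment".

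**The concern.** There is one attribution phrase for three event types, and it directly follows the third. On the SAE-only reading, a clinically relevant grade 3 non-hematologic event counts whatever its cause. These patients receive AML/MDS therapy at the same time, so events with other causes are to be expected. On the whole-list reading, only events at least possibly due to isavuconazole count.

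Two things would be at stake. First, the same patients could give opposite decisions. Suppose 2 of the first 10 have a related event and 4 others have only an unrelated qualifying event. The count is then 6/10 on the SAE-only reading, which meets the Table 3 boundary, and 2/10 on the other, which does not. Second, on the SAE-only reading the rule counts a group that section 12 does not put on the CRF: grade 3 or worse non-hematologic events that are unrelated, not serious and without dose modification. Section 11 names neither the reading nor the data source for the ten-patient summaries.

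**Working it through.** **1. The plan's own figures.** With x toxicities in n patients the posterior is beta(0.6 + x, 1.4 + n − x). The boundary is the smallest x for which Pr(p > 0.3) exceeds 0.9.

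| n | Pr at one below the boundary | Pr at the boundary | Boundary (Table 3) |
|---|---|---|---|
| 10 | 0.8798 | 0.9625 | 6 |
| 20 | 0.8067 | 0.9059 | 9 |
| 30 | 0.8630 | 0.9286 | 13 |
| 40 | 0.8307 | 0.9003 | 16 |
| 50 | 0.8761 | 0.9262 | 20 |
| 60 | 0.8555 | 0.9081 | 23 |
| 70 | 0.8917 | 0.9311 | 27 |
| 80 | 0.8768 | 0.9182 | 30 |
| 90 | 0.8634 | 0.9061 | 33 |

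All nine boundaries match. An exact binomial recursion in cohorts of 10, up to 100 patients, gives early-stopping probabilities of 0.0002, 0.0168, 0.2589, 0.8578 and 1.0000 at true rates 0.1, 0.2, 0.3, 0.4 and 0.6. Average sample sizes are 99.98, 98.65, 83.12, 43.51 and 14.38. Table 4 agrees apart from rounding. The tables depend only on the rate of whatever is counted, so neither reading alters them.

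**2. What the choice of reading could do.** Let r be the rate of related toxicity and u the rate of unrelated qualifying events. Both are assumed, because the documents give neither, and they are taken as independent. The whole-list reading counts at rate r. The SAE-only reading counts at 1 − (1 − r)(1 − u).

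| r | u | SAE-only count rate | P(stop), whole list | P(stop), SAE-only | Average N, SAE-only |
|---|---|---|---|---|---|
| 0.20 | 0.10 | 1 − 0.8 × 0.9 = 0.28 | 0.017 | 0.17 | 88.7 |
| 0.20 | 0.20 | 1 − 0.8 × 0.8 = 0.36 | 0.017 | 0.64 | 59.6 |
| 0.20 | 0.30 | 1 − 0.8 × 0.7 = 0.44 | 0.017 | 0.96 | 31.5 |
| 0.10 | 0.10 | 1 − 0.9 × 0.9 = 0.19 | 0.0002 | 0.012 | 99.0 |
| 0.10 | 0.20 | 1 − 0.9 × 0.8 = 0.28 | 0.0002 | 0.17 | 88.7 |
| 0.10 | 0.30 | 1 − 0.9 × 0.7 = 0.37 | 0.0002 | 0.71 | 55.4 |

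These rows compare the readings with every event captured. They do not measure what is missing from the CRF, since u includes unrelated events already recorded under 3b and 3c.

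**3. What under-capture could do.** If the SAE-only reading were meant and the count came from the CRF alone, a true rate of 0.40 would be seen as 0.40 × 0.75 = 0.30 at 75% capture, or 0.40 × 0.50 = 0.20 at 50%. P(stop) would fall from 0.86 to 0.26 or 0.017. The capture shares are also assumed.

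**4. Which reading the text supports.**

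- The phrase closes an either-or list of singular items. Grammar allows it to govern the last item or all three.
- On the SAE-only reading, an unrelated SAE that was also clinically relevant, grade 3 or worse and non-hematologic would enter through the first limb anyway. The attribution limit on SAEs would then exclude only the remainder.
- Section 10 speaks of toxicity of the drug as a ground for removal, and 4.1.2.3 and item 3a also turn on relatedness.
- Section 1.1 cites 30- and 60-day mortality of 13% and 21% in one mostly older secondary-AML trial (5–10% in mostly younger patients). Against that background, an all-cause reading of a 30% limit that also counts non-fatal grade 3 events is the less likely intent. This is inference.

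**5. Whether the CRF supplies the count on the whole-list reading.** Related non-hematologic events come in under 3a, related SAEs under 3a and 3b, and prolonged myelosuppression through 4a. No gap is left in the first and third limbs, and the second is largely covered.

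**The case for a change.** The strongest argument for a change is that section 12 states attribution item by item, required in 3a and waived in 3b and 3c. The authors could have done the same in section 11, yet attached it to one limb. The word toxicity may suggest a drug effect but does not say so. The rule can halt enrollment, the tabulated differences are large at moderate assumed rates, and one sentence would remove all doubt.

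Part of this stands: no sentence fixes the scope of the phrase, and item 6 of section 12, which ranks protocol language above departmental recording guidelines, does not fix it either. The rest is weaker. The CRF mismatch exists only on the less supported reading. Even there it is narrow, because hospitalization or its prolongation makes an event serious and so recorded under 3b. Nothing confines the ten-patient summary to CRF data, and the trial is run at one centre with AE evaluation scheduled throughout.

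Nor does counting related events hide the others. Events only possibly related count, and every SAE goes to the IND Office regardless of attribution. The large stop probabilities come from assumed rates, and the 2-plus-4 example is built to land on the boundary.

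**Conclusion.** No change to the plan is needed. The scope of the attribution phrase is not stated, but the surrounding text favours the drug-related sense for all three limbs. On that sense the CRF list supplies the count and Tables 3 and 4 apply as printed, for example a 0.02 probability of early stopping at a 20% toxicity rate and 0.86 at 40%. The person preparing the summaries can adopt that reading and record it with the first one.

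The gaps between readings (0.017 against 0.17 to 0.96 at r = 0.20; 0.0002 against 0.012 to 0.71 at r = 0.10) rest on assumed, independent event rates and are not estimates for this trial. The primary endpoint, the incidence of proven or probable fungal infection, is untouched. The conclusion rests on the whole-list reading being the intended one. If the sponsor meant SAEs only, unrelated, non-serious grade 3 or worse non-hematologic events without dose modification would have to come from a source other than the CRF list.

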# Analysis Plan

The primary endpoint is the incidence of proven or probable invasive fungal infections (IFI). The IFI rate will be estimated along with the exact 95% confidence interval.

Secondary endpoints include incidence of IA, overall survival, and time to diagnosis of IFI, etc. Descriptive statistics will be used to summarize all secondary endpoints. The incidence rates of binary secondary endpoints will be estimated, along with the exact 95% confidence intervals. The probabilities of time-to-event outcomes (such as time to death) will be estimated using the method of Kaplan and Meier. Log-rank tests will be used to compare the time-to-event outcomes among subgroups of patients.

Subjects who entered the study and did not take any study drug will not be evaluated for safety. The severity of the toxicities will be graded according to the NCI CTCAE v4.0 whenever possible. We will follow standard reporting guidelines for adverse events. Safety data will be summarized by category, severity and frequency. The proportion of patients with AEs will be estimated among all patients.

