# 4.2.2 Secondary

- 4.2.2.1 Incidence of IA within 100 days of isavuconazole prophylaxis initiation.
- 4.2.2.2 Incidence of other IFIs within 100 days of isavuconazole prophylaxis initiation.
- 4.2.2.3 Rates of treatment success vs. failure (defined above).
- 4.2.2.4 Overall survival.
- 4.2.2.5 Survival without proven or probable IFI.
- 4.2.2.6 Time to death from any cause.
- 4.2.2.7 Time to death related to IFI.
- 4.2.2.8 Time to diagnosis of proven or probable IFI.
- 4.2.2.9 Time to first use of empiric antifungal therapy.
- 4.2.2.10 AEs throughout the duration of isavuconazole prophylaxis until 30 days after the last dose of study drug.

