#### 6.5 Long-term follow-up

The Long-Term Follow-Up schedule begins at the end of treatment assessment and continues until death. All patients who receive at least one dose of study drug will be followed for survival every 6-12 months by telephone call to patient, family, local physician, surface or electronic mail. All patient follow up will continue under DR09-0223. A separate informed consent for that study will be required. Patients may be removed from this current protocol and followed up on the DR09-0223 after completing all protocol related assessments.

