# **10 CRITERIA FOR REMOVAL FROM THE STUDY**

Patients will be removed from the study if:

- 12 weeks have elapsed from the start of therapy, or
- The ANC has recovered to ≥0.5 x 10^9/l and CR with or without complete count recovery has been documented (per ELN criteria), or
- A proven or probable IFI has occurred (as defined by the EORTC/MSG), or
- Unacceptable drug toxicity develops, or
- The patient or investigator decide to withdraw the patient from the study, or
- Patient dies while on study.

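### Kaplan-Meier is planned for every time-to-event outcome with no provision for competing deaths, which slightly overstates the probability of three descriptive secondary endpoints

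*Combined protocol and SAP*

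**What the plan says.** The Analysis Plan in section 11 gives one estimator for all time-to-event outcomes: "The probabilities of time-to-event outcomes (such as time to death) will be estimated using the method of Kaplan and Meier". The same paragraph shows that this reaches beyond survival: "Secondary endpoints include incidence of IA, overall survival, and time to diagnosis of IFI, etc". It also sets the status of these analyses: "Descriptive statistics will be used to summarize all secondary endpoints". Log-rank tests are planned for subgroup comparisons.

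Section 4.2.2 lists three endpoints for which death from another cause is a competing event:

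- 4.2.2.7: "Time to death related to IFI"
- 4.2.2.8: "Time to diagnosis of proven or probable IFI"
- 4.2.2.9: "Time to first use of empiric antifungal therapy"

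Neither section 4 nor section 11 says how a death before the event is treated in these endpoints, and cumulative incidence is not mentioned. The primary IFI rate is handled separately, as a proportion with an exact 95% confidence interval.

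**The concern.** A patient who dies of another cause can no longer have an IFI diagnosed, start empiric antifungal therapy or die of an IFI. Kaplan-Meier with that death censored treats the patient as still able to have the event later, at the same rate as those who remain alive. The result is not the probability of the event among the treated patients, although a probability is what the Analysis Plan promises. If any competing death precedes a later event, 1-KM is above that probability.

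Competing deaths are to be expected. Section 1.1 cites 30- and 60-day mortality of 5-10% in trials of mostly younger patients, 13% and 21% in a trial of secondary AML, and 26.7% early mortality in a population-based series.

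At stake is the accuracy of three descriptive figures, and some avoidable inconsistency. A day-100 1-KM for IFI would tend to exceed the primary proportion computed from the same patients.

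**Working it through.** **The plan's own figures.** The documents give no number for the three endpoints, so there is none to reproduce. The IFI design figures do reproduce: from the Beta(0.1, 1.9) prior and the 0.87 cut-off, the probability of early stopping is 0.2256 at a true rate of 5% (Table 2: 0.23) and 0.8036 at 10% (Table 2: 0.80). These rest on patient counts, so the choice of time-to-event estimator does not touch them.

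**Inputs.**

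- IFI probability *a* = 5%: the rate section 11 expects on isavuconazole.
- All-cause mortality by day 100, *m* = 5%, 10%, 21%: an assumption. The figures come from section 1.1, where they are reported at 30 or 60 days. The 26.7% value is an upper sensitivity case only, since section 1.1 says population-based rates exceed trial rates.
- Empiric antifungal use of 20% or 30%, and IFI-related death of 2%: assumptions, as the documents give no rates.
- Hazards constant over 100 days, follow-up complete to day 100.

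**IFI and empiric use.** With the 100 days as the time unit, the death hazard is μ = −ln(1−m). The event hazard λ solves

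λ/(λ+μ) × [1 − exp(−(λ+μ))] = a, and then 1-KM = 1 − exp(−λ).

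Example, a = 5% and m = 21%: μ = 0.2357, λ = 0.0577, 1-KM = 1 − exp(−0.0577) = 5.6%.

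**IFI-related death.** Here *m* includes the IFI-related deaths. With L = −ln(1−m), 1-KM = 1 − exp(−L × a/m). Example, a = 2% and m = 21%: L = 0.2357, so 1 − exp(−0.2357 × 0.02/0.21) = 2.2%.

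| True probability by day 100 | m = 5% | 10% | 21% | 26.7% (sensitivity) |
|---|---|---|---|---|
| IFI 5% | 5.1% | 5.3% | 5.6% | 5.8% |
| Empiric use 20% (assumed) | 20.5% | 21.0% | 22.3% | 23.1% |
| Empiric use 30% (assumed) | 30.7% | 31.5% | 33.4% | 34.5% |
| IFI-related death 2% (assumed) | 2.0% | 2.1% | 2.2% | 2.3% |

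**Sensitivity to the reading of mortality.** If the mortality figure is taken as death before the event instead of all deaths, 30% empiric use reads 30.9% to 34.3% for 5% to 21% (35.8% at 26.7%). The direction and order of size do not change.

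**Sensitivity to timing.** If all deaths fall in days 0-30, then over *m* = 5% to 26.7% a true 5% IFI reads 5.2% to 6.5% and 30% empiric use reads 31.3% to 38.5%. If the other deaths come only after the events, the excess is zero.

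**Comparison with the primary result.** In 5,000 simulated trials of 100 patients with a true IFI probability of 5%, 1-KM exceeded the crude proportion in 95.9% of trials at m = 5% and 99.3% at m = 21%, and was never below it. The mean excess was 0.13 and 0.61 percentage points. For scale, the exact 95% interval for 5 of 100 is 1.6% to 11.3%.

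**The case against.** **Censoring is inferred.** The plan never says that competing deaths will be censored, and its one example, time to death, is a case where Kaplan-Meier is right. This is true, and the point is worded accordingly. But the sentence covers time-to-event outcomes without exception, time to IFI is named in the same paragraph, and no other provision is made. Following the text as written gives the estimator described.

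**A check already exists.** For IFI, the exact proportion is reported anyway. For antifungal use, the treatment-failure composite in section 4.1.2.3 counts other systemic antifungals given for at least 4 days for suspected IFI, and it will have an exact interval as a binary secondary. That is a partial check, because the composite mixes in other reasons for failure.

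**The effect is small and rests on assumed rates.** Both parts stand. For IFI the excess is 0.1 to 0.6 points up to 21% mortality, well inside the sampling error.

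**A stronger reading to avoid.** Section 6.5 says: "The Long-Term Follow-Up schedule begins at the end of treatment assessment and continues until death". A reader might infer that the overstatement of IFI-related death grows large over that follow-up. Under a formula in which IFI-related deaths stay a constant share of all deaths, a true 2% would read 2.6% with 40% other deaths and 5.3% with 90%. The documents do not support that condition. A 1-KM curve rises only when an IFI-related death occurs, so later deaths from other causes add nothing by themselves. IFI is assessed only to day 100. Section 6.5 describes follow-up for survival, under a separate protocol and consent, and does not mention attributing deaths to IFI. If IFI-related deaths fall within the first 100 days, the figure stays at 2.0% to 2.3% however many patients die later.

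**Conclusion.** The point holds as a minor one. For endpoints 4.2.2.7 to 4.2.2.9 the planned estimator, used in the usual way, overstates the event probability whenever a competing death precedes a later event. Up to 21% mortality the excess is at most about 0.6 points for IFI, 3.4 points for an assumed 30% empiric use and 0.2 points for an assumed 2% IFI-related death. At the 26.7% sensitivity value it is 0.8, 4.5 and 0.3 points. These sizes rest on constant hazards, borrowed mortality figures and assumed event rates. The direction does not depend on them, though the excess can be zero.

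It should not be read as a flaw in the trial's main result. The primary proportion, the binary secondaries and both stopping rules do not use Kaplan-Meier. Overall survival, IFI-free survival and time to death from any cause count death as an event, so Kaplan-Meier is appropriate there. No decision rule uses the three affected endpoints.

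**What to change.** Amend the Analysis Plan to:

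- estimate 4.2.2.7, 4.2.2.8 and 4.2.2.9 by cumulative incidence (Aalen-Johansen) at a stated horizon such as day 100;
- name the competing event: death without the event for IFI and for empiric antifungal use, and non-IFI death for IFI-related death;
- state how an IFI that precedes empiric therapy is handled in 4.2.2.9, because section 10 takes patients off study once "A proven or probable IFI has occurred";
- keep Kaplan-Meier for overall survival, IFI-free survival and time to death from any cause;
- keep the log-rank test for the three endpoints, described as a comparison of cause-specific hazards.

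With complete follow-up to day 100, the cumulative incidence of IFI then equals the primary proportion, so the two reported figures agree. The cost is one or two sentences and standard software; no new data are needed and neither the sample size nor the monitoring changes.
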